10.11.2.2. Liver Chemistry Increased Monitoring Criteria with Continued Study Intervention

Liver Chemistry Increased Monitoring Criterion and Actions with Continued Study		
Intervention		
Criterion	Actions	
ALT or AST-≥3xULN and <5xULN and total bilirubin <2xULN or INR<1.5 (if measured), without symptoms believed to be related to liver injury or hypersensitivity, and who can be monitored weekly for 4 weeks	 Notify the sponsor within 24 hours of learning of the abnormality to discuss participant safety PARTICIPANT CAN CONTINUE STUDY INTERVENTION. Participant must return weekly for repeat liver chemistry tests (ALT, AST, alkaline phosphatase, total bilirubin) until the abnormalities resolve, stabilize or return to baseline 	

CONFIDENTIAL – FOIA Exemptions Apply in U.S.

• If at any time, the participant meets liver chemistry stopping criteria, proceed as described in Section 10.11.2.1 Liver Follow-up Assessments
• If, after 4 weeks of monitoring, ALT or AST - <3xULN and total bilirubin <2xULN, monitor participants twice monthly until liver chemistry tests resolve, stabilize, or return to baseline

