10.11.1.1. ALT or AST

Liver Chemistry Stopping Criteria		
ALT or AST- ≥5xULN, or		
ALT or AST- ≥3xULN persists for ≥4 weeks, or		
ALT or AST- $\geq 3x$ ULN and total bilirubin $\geq 2x$ ULN (or at least a doubling of direct bilirubin		
in known Gilbert's syndrome), or		
ALT or AST- \geq 3xULN and international normalized ratio (INR) \geq 1.5, if INR measured, or		
ALT or AST- ≥3xULN associated with symptoms (new or worsening) believed to be related to		

Dengue infection can alter/increase liver enzymes in the infected individual. For this reason, if any of the above liver chemistry stopping criteria are met, investigator together with sponsor will decide on the discontinuation of the study intervention. If a participant is discontinued, they will not be restarted or rechallenged again.

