10.11.2. Follow-up Assessments

- **Repeat testing** to confirm laboratory abnormalities within 24 hours prior to stopping, unless safety is considered at risk by the sponsor and/or investigator
- Report the event to the sponsor within 24 hours to decide on discontinuing study intervention

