10.11.2.1. Liver Follow-up Assessments with discontinued Study Intervention

If liver chemistry stopping are deemed to be possibly related to the drug intervention by the investigator and sponsor, the below monitoring and follow up assessments apply:

Suggested Actions, Monitoring and Follow-up Assessments		
Actions	Follow-up Assessments ^f	
 Complete the CRF according to CRF completion guidelines, and complete an SAE data collection tool if the event also met the criteria for an SAE^b Perform follow-up assessments as described in the Follow Up Assessment column Monitor the participant until liver chemistry test abnormalities resolve, stabilize, or return to baseline (see MONITORING) 	 Viral hepatitis serology^d Obtain INR and recheck with each liver chemistry assessment until the transaminases values show downward trend Obtain blood sample for PK analysis after the most recent dose^e Obtain serum CPK, lactate dehydrogenase (LDH), GGT, 	

MONITORING:

If ALP <2 x ULN, ALT or AST-≥3xULN AND total bilirubin ≥2xULN (or at least a doubling of direct bilirubin in known Gilbert's syndrome) or INR >1.5 (if measured):

- Repeat liver chemistry tests (include ALT, AST, ALP, total and direct bilirubin and INR) and perform liver event follow-up assessments within 24 hours
- Monitor participant twice weekly until liver chemistry test abnormalities resolve, stabilize, or return to baseline
- A specialist or hepatology consultation is recommended

If ALT or AST-≥3xULN AND total bilirubin <2xULN and INR ≤1.5:

- Repeat liver chemistry tests (include ALT, AST, alkaline phosphatase, total and direct bilirubin and INR) and perform liver chemistry follow-up assessments within 24 to 72 hours
- Monitor participants weekly until liver chemistry abnormalities resolve, stabilize, or return to baseline

- glutamate dehydrogenase (GLDH), and serum albumin
- Fractionate bilirubin
- Obtain complete blood count with differential to assess eosinophilia
- Record the appearance or worsening of clinical symptoms of liver injury, or hypersensitivity, on the CRF as per CRF completion guidelines
- Record use of concomitant medications (including acetaminophen, herbal remedies, recreational drugs and other over-thecounter medications)
- Record alcohol use on the CRF as per CRF completion guidelines

If ALT or AST ≥3xULN AND total bilirubin ≥2xULN or INR >1.5 (if measured) obtain the following in addition to the assessments listed above:

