- Anti-nuclear antibody, anti-smooth muscle antibody, Type 1 anti-liver kidney microsomal antibodies, and quantitative total IgG or gamma globulins
- Serum acetaminophen adduct assay, when available, to assess potential acetaminophen contribution to liver injury in participants with definite or likely acetaminophen use in the preceding week
- Depending on availability, liver imaging (ultrasound, magnetic resonance, or computerized tomography) and/or liver biopsy to evaluate liver disease; complete CRF as per CRF completion guidelines
- Liver biopsy may be considered and discussed with local specialist if available:
 - In participants when serology raises the possibility of autoimmune hepatitis (AIH)

 In participants when suspected DILI progresses or fails to resolve on withdrawal of study intervention
 In with acute or chronic atypical presentation
 If liver biopsy conducted complete CRF as per CRF completion guidelines

- Serum bilirubin fractionation should be performed if testing is available. If serum bilirubin fractionation is not immediately available, discontinue study intervention if ALT ≥3xULN and total bilirubin ≥2xULN. Additionally, if serum bilirubin fractionation testing is unavailable, record the absence/presence of detectable urinary bilirubin on dipstick which is indicative of direct bilirubin elevations suggesting liver injury.
- All events of ALP <2 x ULN, ALT or AST ≥3 x ULN and total bilirubin ≥2xULN (or at least a doubling of direct bilirubin in known Gilbert's syndrome) or ALP <2 x ULN, ALT or AST ≥3 x ULN and INR >1.5 (if measured) may indicate severe liver injury (possible 'Hy's Law') and must be reported to sponsor in an expedited manner and as an SAE if SAE criteria are met (excluding studies of hepatic impairment or cirrhosis). The INR stated threshold value will not apply to participants receiving anticoagulants.
- New or worsening symptoms believed to be related to liver injury (such as fatigue, nausea, vomiting, right upper quadrant pain or tenderness, or jaundice) or hypersensitivity (such as fever, rash or eosinophilia).
- Includes: hepatitis A IgM antibody; HBsAgG and HBcAB; hepatitis C RNA; cytomegalovirus IgM antibody; Epstein-Barr viral capsid antigen IgM antibody (or if unavailable, heterophile antibody or monospot testing); and hepatitis E IgM antibody.

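### The liver 'can continue' row joins bilirubin and INR with 'or', so two of four combinations also meet a stopping criterion; 'and' removes that overlap

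*Protocol*

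**What the plan says.** Protocol Appendix 11 (Section 10.11) has a stopping list and a row for continuing with extra monitoring.

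- **Stopping list, Section 10.11.1.1.** With ALT or AST at or above 3xULN, each of these is a criterion in its own right: total bilirubin at or above 2xULN (or doubled direct bilirubin in known Gilbert's syndrome); INR at or above 1.5 if measured; related symptoms; or "ALT or AST- ≥3xULN persists for ≥4 weeks". ALT or AST at or above 5xULN is a criterion alone. Because dengue itself can raise liver enzymes, "investigator together with sponsor will decide on the discontinuation of the study intervention".
- **Continue row, Section 10.11.2.2.** The participant must have ALT or AST from 3xULN to below 5xULN, be suitable for weekly monitoring over four weeks, and satisfy "total bilirubin <2xULN or INR<1.5 (if measured), without symptoms believed to be related to liver injury or hypersensitivity". The action is that dosing can continue, with the sponsor notified within 24 hours and weekly ALT, AST, alkaline phosphatase and total bilirubin. INR is not on that list. A later bullet sends anyone who meets a stopping criterion, at any time, to Section 10.11.2.1.
- **Body of the protocol.** Section 7.1 lists abnormal liver tests under Appendix 11 among the reasons for which study intervention must be discontinued. Section 7.1.2 requires the investigator to stop when an Appendix 11 condition is met, after consulting the sponsor.
- **Related wording, Section 10.11.2.1.** The lower-risk monitoring group is written "If ALT or AST-≥3xULN AND total bilirubin <2xULN and INR ≤1.5".

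**The concern.** The continue row should hold only participants who meet no stopping criterion. Because bilirubin and INR are separate stopping criteria, its entry condition has to require both to be below their limits. As worded, either one is enough, so the same laboratory result can place a participant under an action line that permits dosing and also in the stopping list.

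The two routes also differ in follow-up. The continue row has weekly chemistry without INR. Section 10.11.2.1, where the abnormality is judged possibly drug-related, rechecks INR with each liver assessment until transaminases trend down. When alkaline phosphatase is below 2xULN and either bilirubin is at or above 2xULN or INR is above 1.5, it adds repeat tests within 24 hours, twice-weekly monitoring and a recommended specialist consultation. Its footnotes treat those patterns as possible Hy's Law events. A site reader who stops at the entry criterion would apply the lighter schedule to a pattern that the protocol elsewhere treats as possible severe liver injury.

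**Working it through.** The documents give no figure to reproduce, so the check is a truth table.

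**Inputs.** ALT or AST is fixed from 3xULN to below 5xULN, with no related symptoms, no known Gilbert's syndrome and less than four weeks' persistence.

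- Stop (Section 10.11.1.1) = bilirubin ≥2xULN, or INR ≥1.5 if measured.
- Continue as written (Section 10.11.2.2) = bilirubin <2xULN, or INR <1.5.
- Continue with 'and' = bilirubin <2xULN and INR <1.5.
- If INR is not measured, bilirubin alone decides. This is my reading of the 'if measured' qualifier.

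| Bilirubin | INR | Stop | Continue as written | Continue with 'and' |
|---|---|---|---|---|
| <2xULN | <1.5 | no | yes | yes |
| <2xULN | ≥1.5 | yes | **yes** | no |
| ≥2xULN | <1.5 | yes | **yes** | no |
| ≥2xULN | ≥1.5 | yes | no | no |
| <2xULN | not measured | no | yes | yes |
| ≥2xULN | not measured | yes | no | no |

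**INR measured (first four lines).** As written, 3 of 4 combinations enter the row, 3 of 4 meet a stopping criterion, and 2 of 4 do both. With 'and', 1 enters, 3 stop, 0 do both and 0 do neither.

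**Adding INR not measured.** The overlap is 2 of 6 as written and 0 of 6 with 'and', again with none uncovered.

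**Other readings of 'or'.** Strict precedence of 'and' over 'or' gives the same cells within this ALT/AST band. An exclusive 'or' keeps the same two overlaps and also leaves the first line without a rule. No reading of 'or' removes the conflict.

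**Limit of the fix.** If doubled direct bilirubin in known Gilbert's syndrome, or persistence for at least four weeks, is present, all four INR-measured lines meet a stopping criterion. The overlap is then 3 of 4 as written and 1 of 4 with 'and' (bilirubin <2xULN, INR <1.5). Persistence has little reach during dosing. The first scheduled chemistry after baseline is Day 13 and dosing ends on Day 28, 15 days later, so on scheduled samples the elevation would have to be present at or near baseline.

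**Is the INR-measured state routine?** Yes. Appendix 8 lists INR in the coagulation panel, and the Schedule of Activities draws coagulation and chemistry together on Days 1, 13, 28 and 50.

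**The case against.** The best answer is that the protocol already settles the conflict. The continue row's own actions redirect anyone who meets a stopping criterion at any time, and that includes the moment of entry. Sections 7.1 and 7.1.2 are body text that requires stopping, whereas the appendix is titled as suggested actions and the continue line is permissive. Sponsor contact within 24 hours applies on both routes; on the stopping route it reads "Report the event to the sponsor within 24 hours to decide on discontinuing study intervention". A careful reader would handle both disputed combinations in the same way whichever connector is used.

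Most of that stands and is why the point is minor. It does not make the entry criterion right: the redirect has to undo an admission that should not have been made, and the action line conflicts with Sections 7.1, 7.1.2 and 10.11.1.1.

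Three stronger readings are tempting, and the documents do not support them:

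- A reader might infer that the row overrides the stopping rules. It does not: the stopping list is intact and the redirect gives it precedence.
- A reader might infer that the INR combination is protected only by the redirect, because the separate footnote instruction, "If serum bilirubin fractionation is not immediately available, discontinue study intervention if ALT ≥3xULN and total bilirubin ≥2xULN", covers bilirubin and names ALT only. INR of at least 1.5 is itself a listed criterion, so Sections 7.1, 7.1.2 and 10.11.1.1 apply to it directly. When alkaline phosphatase is below 2xULN, INR above 1.5 also calls for expedited reporting to the sponsor.
- A reader might infer from the joint decision that sponsor contact is neutral on stopping. Sections 7.1 and 7.1.2 set stopping as the requirement, with consultation attached.

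The wording in Section 10.11.2.1 is also an imperfect comparator. Its INR limit is ≤1.5 rather than <1.5, it has no 5xULN ceiling, and it sets monitoring frequency after discontinuation. It supports 'and' as the intended connector and nothing more.

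**Conclusion.** The entry criterion in Section 10.11.2.2 is wrong as written. With INR measured, it admits two of four bilirubin/INR combinations that already meet a stopping criterion. The result assumes ALT or AST in the row's band, no related symptoms, and neither the Gilbert's nor the persistence criterion present. The counts are logical combinations, not participants; the documents give no frequency, and none is implied.

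Severity is minor. The redirect in the same row and the stopping requirements elsewhere limit the harm to a reader who acts on the entry criterion alone. No efficacy or safety analysis depends on it. SAP Section 1 reports that the study ended on 02 October 2024 for portfolio reasons and not for safety concerns, so the correction serves the record and any reuse of this appendix.

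**What to change.** In Section 10.11.2.2, change the connector so that the condition reads *total bilirubin <2xULN and INR <1.5 (if measured)*. Within the inputs above, the row then becomes the exact complement of the bilirubin and INR stopping criteria.

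The edit does not reach the Gilbert's or four-week persistence criteria, which stay governed by the redirect sentence in the same row. It also does not add INR to the weekly test list; whether to do so is a separate choice for the sponsor.

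The cost is one word of protocol text. No endpoint, analysis or assessment changes.

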symptoms (systemic solicited AEs)														in a diary by the participant. In case a particular systemic
														solicited AE was not observed at time of recording but occurs
														later that day, the participant should record this. In case the
														systemic solicited AE is fever, oral body temperature should
D. 1. days and ma	37	37	37	37	X	V	37	X	X	X	37	X	37	also be recorded.
Body temperature	X	Χ	X	Λ	X	Λ	Λ	Λ	Λ	Λ	Λ	Α.	Λ	Body temperature is to be measured orally in the absence of antipyretic medication, or at least 4 hours after the last intake
														of antipyretic medication (if applicable).
														Will be recorded daily in a diary by the participant (preferably
														at the same time each day) and in case of feeling feverish.
														Will be added to the CRF by study site personnel in case the
														oral body temperature is $\geq 37.5^{\circ}$ C (99.5°F).
Clinical Laboratory Tests									I	1	1		 	joint cour verification is to the control of the co
Blood sample collection for hematology	O g										Π		X	
Blood sample collection for serum	Oe, g												X	
chemistry														
Blood sample collection for coagulation	0 e, g												X	
Urine sample collection for urinalysis	0												X	Urinalysis including dipstick, microscopic sediment
											L			examination, and quantitative protein determination.
Pharmacokinetics														
Blood sample collection for PK	0		X		X				X				X	Blood collections for PK assessments should be kept as close to the
														specified time as possible.
														For participants in the PK Substudy, see also Section 1.3.2.5,

Phase	Double-blind Prophylactic Dosing 1 2 3 4 5 6 7 8 9 10 11 12 13													
Visit Day	Visit Day 1 2 3					6	7	8	9	10	11	12	13	
Visit Window					± 1d				± 1d	ı			± 1	d
Study Procedure														Notes
														Pharmacokinetic Substudy.
Pharmacogenomics (DNA)														
Blood sample collection for host genetics analyses	•													An optional DNA sample for research (where local regulations permit) may be collected after providing consent in a separate ICF. The sample should preferably be collected before the first dose of study intervention; however, if necessary, it may be collected at a later time point without constituting a protocol deviation.
Biomarkers														
Blood sample collection for host RNA assessments	0				X									

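### The liver step-down rule in Protocol 10.11.2.2 joins ALT and AST with 'or' where it needs 'and', so it can be met while one enzyme is still at 3xULN or more (low severity)

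*Protocol*

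**What the plan says.** Protocol Appendix 11 covers liver safety. Four rules bear on this point.

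- **Entry to increased monitoring (10.11.2.2, Criterion).** It applies at "ALT or AST-≥3xULN and <5xULN and total bilirubin <2xULN" (or an INR limit, if measured), without related symptoms, in a participant "who can be monitored weekly for 4 weeks".
- **Weekly tests (10.11.2.2, Actions).** "Participant must return weekly for repeat liver chemistry tests (ALT, AST, alkaline phosphatase, total bilirubin) until the abnormalities resolve, stabilize or return to baseline".
- **Override (10.11.2.2, the bullet just before the step-down).** "If at any time, the participant meets liver chemistry stopping criteria, proceed as described in Section 10.11.2.1 Liver Follow-up Assessments". One stopping criterion in 10.11.1.1 is "ALT or AST- ≥3xULN persists for ≥4 weeks".
- **Step-down (10.11.2.2, last bullet).** "If, after 4 weeks of monitoring, ALT or AST - <3xULN and total bilirubin <2xULN, monitor participants twice monthly".

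Section 10.11.2.1 applies under the condition "If liver chemistry stopping are deemed to be possibly related to the drug intervention by the investigator and sponsor". It then asks for weekly monitoring when bilirubin is below 2xULN and INR is at most 1.5. It asks for twice-weekly monitoring when ALP is below 2xULN, an enzyme is at 3xULN or more, and bilirubin is at 2xULN or more or INR exceeds 1.5.

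**The concern.** Entry is triggered by either enzyme, so leaving that state should require both enzymes to be below the threshold. The step-down keeps the same connector, and a participant with one enzyme still in the entry band can therefore satisfy it. A site applying the last bullet word for word could move that participant to twice-monthly tests while the entry rule still points to weekly ones.

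What is at stake is how often an unresolved elevation is retested. The Schedule of Activities (Protocol 1.3.2.2 and 1.3.2.3) plans serum chemistry on Days 1, 13, 28 and 50 and none later. For a participant who completes dosing, after Day 50 this table sets the retest frequency.

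**Working it through.** **Logic.** Entry on the enzymes is (ALT ≥3 or AST ≥3), each below 5xULN. The negation of (ALT ≥3 or AST ≥3) is (ALT <3 and AST <3). The bullet instead uses (ALT <3 or AST <3).

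States at week 4, in multiples of ULN, with bilirubin <2xULN, INR <1.5 and no symptoms:

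| ALT / AST | Entry met | Step-down as written | Step-down with both <3 | Stopping criterion if high for ≥4 weeks | Stopping criterion if not |
|---|---|---|---|---|---|
| 2 / 2 | no | yes | yes | no | no |
| 4 / 2 | yes | yes | no | yes | no |
| 2 / 4 | yes | yes | no | yes | no |
| 4 / 4 | yes | no | no | yes | no |
| 5.5 / 2 | no | yes | no | yes | yes |

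The two mixed states (4/2 and 2/4) meet entry and step-down together. If the elevation has lasted 4 weeks, the override applies. If it has not, no stopping criterion is met and the overlap stands. With both enzymes required, no listed state meets entry and step-down together.

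**When the bullet can operate.** The last dose is on Day 28 (Protocol 4.1: 2 days of loading plus 26 of maintenance). Four weeks from a Day 1 finding is 1 + 28 = Day 29, and from a Day 13 finding 13 + 28 = Day 41. The bullet therefore acts only after dosing.

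**Illustration of a late rise (hypothetical values).** ALT is 3.5xULN on Day 13. Both enzymes are <3xULN on Day 27. AST is 3.6xULN on Day 34. On Day 41 ALT is 2.0 and AST 3.8xULN. AST has been high for 41 − 34 = 7 days, short of 28, so the persistence criterion is not met. The step-down is met on Day 41. It is met even if the enzyme condition is taken to mean only the enzyme that started monitoring, since that was ALT.

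**Number of checks after Day 41, counted to the last visit on Day 90.** Twice monthly is assumed to mean every 15 days, range 14 to 16.

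- Weekly: Days 48, 55, 62, 69, 76, 83, 90 = 7, or 8 if the scheduled Day 50 sample is separate.
- Every 15 days: Days 56, 71, 86, plus Day 50 = 4.
- Every 14 days: Days 55, 69, 83, plus Day 50 = 4.
- Every 16 days: Days 57, 73, 89, plus Day 50 = 4.
- After Day 50 only: 6 weekly checks against 3.

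**Delay in the illustration.** AST completes 4 weeks at ≥3xULN on 34 + 28 = Day 62. Weekly testing shows this on Day 62. Twice-monthly testing shows it on Day 71 (Day 69 to 73), a delay of 71 − 62 = 9 days (7 to 11).

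**The case against.** The best defence is that the table, read in order, already covers the common case. A participant still at 3xULN or more after 4 continuous weeks meets a stopping criterion, and the override sits directly above the step-down. This stands, and it confines the point to elevations that have not lasted 4 weeks. The override's destination has its own limit, because 10.11.2.1 applies only when the event is judged possibly drug-related. That is a separate matter, which rewording the step-down does not settle.

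The late rise can also be read as a new trigger with its own 4-week clock, so that step-down would not be due on Day 41. That reading is reasonable, but the table does not state it. There is a further doubt whether a first AST rise on Day 34 belongs in a table headed for continued study intervention, since dosing has ended. Both points make the illustration depend on interpretation. Neither makes the written condition correct.

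The practical backstops also stand. The appendix is titled as suggested actions, the sponsor is notified within 24 hours at entry, and Protocol 8.2 allows extra safety assessments and requires follow-up of clinically significant abnormalities persisting at study end. These limit harm, but they do not say which frequency applies.

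**Conclusion.** The step-down condition is wrong as written, at low severity. It permits twice-monthly checks with one enzyme still in the entry band, and the uncovered case is a late rise or rebound without 4 continuous weeks of elevation. In the worked case this means 3 checks instead of 6 between Day 50 and Day 90, and recognition 7 to 11 days later. Those figures assume 14- to 16-day spacing, a Day 13 start and the literal reading. Day 90 is only a counting limit, since the table sets no end date. The number of participants affected cannot be derived from the documents.

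A reader might infer that the bullet contradicts the weekly-testing instruction. The documents do not support that. Weekly testing also ends when values stabilize or return to baseline, the entry criterion itself envisages 4 weeks of weekly tests, and a lower frequency afterwards is a planned taper. Both enzymes at 2.5xULN would move to twice monthly under either wording.

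Nor does the bullet force a site to relax monitoring, or touch dosing, endpoints or analysis.

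**What to change.** In the last Actions bullet of 10.11.2.2, replace the enzyme condition with *ALT and AST are both <3xULN*. Leave the bilirubin limit, the twice-monthly frequency and the end condition as they are.

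Do not add an unqualified instruction to continue weekly otherwise. It would clash with 10.11.2.1 for participants who meet a stopping criterion, for example where bilirubin is at 2xULN or more with ALP below 2xULN and twice-weekly checks are specified. If such a clause is wanted, it should except anyone who meets a stopping criterion and send them to 10.11.2.1.

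The cost is one clause in Appendix 11. The study ended early on 02 October 2024 (SAP section 1), so the main value is in correcting the text before it is reused.
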